# 5.3. Missing data

Participants with missing data on BCG, YF-17D, Ty21a, HPV and Td vaccination and/or measurement for primary endpoints will be excluded from the respective analysis as detailed in the analysis population section. There will be no imputation of missing data.

# 5.4. Statistical software

The analysis will be carried out using Stata version 12 or above. Other packages such as R and SAS may be used if necessary.

# 5.5. Sample tables

# 5.5.1. Baseline characteristics of study participants

### Table 2: Baseline characteristics of study participants by trial arm

	D	Р	Placebo	
Characteristic	n	Col%	n	Col%
Sex (Male)				
Age				
School				
Good hope day and boarding				
Etc				
Malaria infection status				
Infected				
S. mansoni infection status				
Infected				
Etc				

### 5.5.2. Comparison of primary outcome responses between trial arms

Table 3: Differences in responses between DP and Placebo arms at week 8 for BCG, YF-17D, Ty21a, HPV and week 52 for Td.

	DP	Placebo			
Vaccine	Mean (SD)**	Mean (SD)**	Mean difference***	95% CI	P value*
BCG					
YF-17D					
Ty21a					
HPV					
Td					

\*P values reported from unpaired t test

\*\* If data are not normally distributed, median (IQR) or geometric mean (SD) will be presented

\*\*\* If data not normally distributed, Geometric Mean Ratios (GMR) will be presented

# 5.5.3. Comparison of secondary outcome responses between trial arms

Table 4: Proportions with protective immunity between DP and placebo arm participants at 4 weeks post the corresponding vaccination.

	DP		Placebo		Risk difference (95% Cl)	P value*
	n/N	Col %	n/N	Col %		
Protective neutralising antibody (YF)						
Protective IgG levels (TT)						
Seroconversion rates (Ty21a)						

\*P values reported from chi square test

Table 5: Priming versus boosting: Comparison of HPV responses after priming and boosting doses

	4 weeks after priming dose, mean (SD)**	4 weeks after boosting dose, mean (SD)**	P value*
Arm			
DP			
Placebo			

\*P values reported from paired t test

\*\* If data are non-normally distributed, median (IQR) or geometric mean (SD) will be presented

Table 6: Comparison of current malaria infection between DP and placebo arms at weeks -8, 0, 4, 8 and 52.

	Scr	eening (wee	ek -8)#	Week 0 #				
	DP	Placebo	P value*	DP	Placebo	P value*	Estimate	P value**
							(95% CI)**	
	n(Col%)	n(Col%)		n (Col%)	n(Col%)			
Malaria infection status								
Positive								
Negative								
Malaria infection intensity								
Light								
Medium								
Heavy								

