# 2. Study Methods

# 2.1. Trial design

This trial is a randomised, double-blind, placebo-controlled, parallel group trial comparing effect of monthly preventive treatment of malaria with dihyrodartemisinin-piperaquine (DP) versus placebo on vaccine response outcomes. Treatment allocation is a 1:1 ratio for the trial intervention.

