### Timing of secondary outcomes

*Protective immunity:* Proportions with protective neutralising antibody (YF), i.e. neutralising antibody>1/5; protective IgG levels (TT), i.e. IgG>0.1 IU/ml; seroconversion rates (Ty21a) at four weeks post the corresponding immunisation (week 8).

*Response waning:* Primary outcome measures for all vaccines repeated at week 52 except for Td whose primary outcome responses are measured at week 52.

*Priming versus boosting:* HPV vaccine responses four weeks after the priming dose (week 8) and 24 weeks after the boosting dose (week 52).

Current malaria infection status and intensity at screening (week -8), weeks 0, 4, 8, 52.

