# 3. Statistical Principles

# 3.1. Level of statistical significance

All applicable statistical tests will be 2-sided. All tests will be performed using a 5% significance level. 95% confidence intervals will be presented.

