# Analysis population for the secondary outcomes

*Protective immunity:* Analysis population for YF, Ty21a and Td protective immunity will include all enrolled participants who receive the respective vaccine (YF-17D, Ty21a at week 4, Td vaccine at week 28) and have responses to the respective vaccines at 4 weeks post vaccination for YF-17D, Ty21a and 24 weeks post Td vaccination.

*Response waning:* Analysis population will include all enrolled participants who receive any of BCG, YF-17D, Ty21a, HPV and Td vaccines; have corresponding responses to any of these vaccines at weeks 8, 28 (for Td vaccine) and 52 post vaccination.

*Priming versus boosting:* Analysis population will include all enrolled participants who receive a priming dose of HPV vaccine at week 4 and a boosting dose at week 28 and have corresponding responses to the vaccine (at weeks 8 and 52).

Current malaria infection status and intensity: Analysis population will include all enrolled participants who have serum/plasma samples and corresponding results at any of these time points; baseline (week -8), on immunisation days (weeks 0, 4, 8 and 28), and on primary (weeks 8 and 52) and secondary endpoint days (week 52).

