# 4.2. Baseline characteristics

Participants will be described with respect to their baseline characteristics including age, sex, school, location of birth, prior vaccination status, malaria infection status both overall and separately for each arm.

Categorical variables will be summarised by numbers and percentages. Continuous variables will be summarised by mean, SD and range if data are normal or median, IQR and range if data are skewed. No statistical tests will be done to compare baseline characteristics between arms.

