# 5.2.2. Analysis of secondary objective outcome measures

*Protective immunity:* Proportions of participants in each category will be presented by trial arm and comparisons between trial arms will be made using chi square test.

*Response waning:* Area under the curve will used for analysis of response waning. Response measurements from weeks 8 and 52 will be used for this analysis.

*Priming versus boosting:* Mean HPV responses will be presented, and a paired t test will be used to compare HPV responses at weeks 8 and 52. In addition, a linear regression model including a time\*trial arm interaction term will be fitted to assess whether the intervention has a differential effect on the response to priming and than to boosting.

*Current malaria infection and intensity:* Proportions of participants with malaria infection will be presented at each timepoint by trial arm and comparisons between trial arms will be made using chi square test. At each timepoint, the means (SD) of malaria infection intensity will be presented by trial arm, and comparisons between trial arms will be made using unpaired t-tests. For both malaria infection status and intensity, Generalised Estimating Equations (GEE) will be used to estimate and compare malaria status and intensity changes between the trial arms.

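### Week -8 malaria status is tested between arms although section 4.2 bars baseline tests, and the GEE for this outcome leaves its reference visit, baseline covariate and population unstated

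*SAP*

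**What the plan says.** Section 4.2 includes malaria status in the list of baseline characteristics to be described overall and by arm, and closes with the rule "No statistical tests will be done to compare baseline characteristics between arms". The secondary-outcome part of section 3.3 identifies the baseline visit when it lists the malaria measurement times: "baseline (week -8), on immunisation days (weeks 0, 4, 8 and 28" and so on.

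Other sections treat the same visit as an outcome time.

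- Section 2.7 gives the secondary malaria outcome as "Current malaria infection status and intensity at screening (week -8), weeks 0, 4, 8, 52".
- Section 5.2.2 compares the arms at every timepoint, by chi-square test for infection status and unpaired t test for intensity. It adds that GEE "will be used to estimate and compare malaria status and intensity changes between the trial arms".
- Section 5.5.3 has the shell "Table 6: Comparison of current malaria infection between DP and placebo arms at weeks -8, 0, 4, 8 and 52". Its screening columns end in a P value footnoted as chi-square. Its week 0 columns have that P value plus an estimate and P value from the GEE.

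The SAP names no reference visit, mean model or covariates for the GEE. Section 5.2.1 considers baseline adjustment for the primary vaccine outcomes only. Section 3.3 restricts the primary analysis to participants who were PCR-positive at baseline, in order to study the effect of removing parasites. It describes the malaria-outcome population as all enrolled participants with samples and results.

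**The concern.** Malaria status at week -8 cannot be both a baseline characteristic that is not tested and an outcome visit that is. A reader of Table 6 could take a small screening P value as evidence about DP, or a large one as proof of balance; it is neither.

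The second issue is how the later visits are compared. The malaria outcome shows whether DP separated the arms in infection around vaccination, and the vaccine results are hard to interpret without that. Suppose the vaccine comparison in the PCR-positive group is null. Malaria may then have no reversible effect on responses, or the arms may have differed little in infection at weeks 0 to 8. Telling these apart needs a clear DP-placebo estimate at each visit, including in the group used for the primary analysis. The SAP does not say how the GEE yields such an estimate, does not use the week -8 value to sharpen it, and does not say plainly whether it will be reported in that group.

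**Working it through.** **1. The contradiction.** No arithmetic is needed.

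| Place in SAP | Treatment of week -8 malaria |
|---|---|
| 3.3, secondary outcomes | called baseline |
| 4.2 | malaria status is a baseline characteristic; no between-arm tests |
| 2.7 | a time point of the secondary outcome |
| 5.2.2 | arms tested at each timepoint |
| Table 6 | chi-square P value under screening |

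The first two rows cannot be followed together with the last three.

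**2. What the week -8 test can show.** Allocation is randomised 1:1 and "All tests will be performed using a 5% significance level". Under valid randomisation any week -8 difference is due to chance, so each such test falls below 0.05 about 5% of the time whatever DP does.

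**3. Precision.** Let rho be the correlation between the week -8 and follow-up values. The SAP gives none, so rho is assumed. For a linear contrast with equal variances, relative to follow-up alone = 1:

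- change from week -8: 2(1 - rho)
- week -8 as covariate: 1 - rho^2
- change / covariate: 2(1 - rho)/(1 - rho^2) = 2/(1 + rho)
- follow-up alone / covariate: 1/(1 - rho^2)

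| rho | change | covariate | change / covariate | follow-up alone / covariate |
|---|---|---|---|---|
| 0.2 | 1.60 | 0.96 | 1.67 | 1.04 |
| 0.3 | 1.40 | 0.91 | 1.54 | 1.10 |
| 0.5 | 1.00 | 0.75 | 1.33 | 1.33 |
| 0.8 | 0.40 | 0.36 | 1.11 | 2.78 |

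The covariate analysis is the most precise in every row. Below rho = 0.5 a change contrast is also less precise than follow-up alone; above 0.5 that order reverses.

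**4. Check on binary data.** An illustrative simulation used 340 participants, assumed prevalences and a realised correlation of about 0.25. The mean standard errors of the risk difference were 0.0631 (change), 0.0501 (follow-up alone) and 0.0485 (covariate).

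- Change / covariate: (0.0631/0.0485)^2 = 1.69; the formula gives 2/1.25 = 1.60.
- Follow-up alone / covariate: (0.0501/0.0485)^2 = 1.07; the formula gives 1/(1 - 0.0625) = 1.07.

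**5. The PCR-positive group.** Section 2.2 gives its size: 341 x 0.6 = 204.6, or 102 per arm, and 102.3 x 0.8 = 81.8, the stated 82 per arm. Table 1 of the SAP reproduces within one percentage point in all 24 cells, so no stated figure is in dispute.

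If week -8 status in Table 6 is the same PCR result that defines this group, prevalence at week -8 is 100% in both arms. The chi-square then has an empty row. A logistic GEE that keeps week -8 as an outcome row has no negatives at that visit. In a simulated set of 204 such participants the intercept ran to about 27.6, and the standard errors of all terms, including arm-by-time, exceeded 5,000. In the corresponding set of all enrolled (n = 340) the arm-by-time standard error was 0.31. Intensity still varies among positives and does not have this problem.

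**The case against.** The strongest reply is that only one redundant P value is plainly wrong. No treatment-effect estimate depends on it, and Table 2 already shows malaria status by arm without a test. The first part is right: the contradiction does not bias any comparison of DP with placebo.

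Three stronger readings are tempting, and the SAP does not support them.

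- *DP is judged only on change from week -8.* The word 'changes' and the Table 6 layout, where GEE estimates start at week 0, point to week -8 as the reference, but the SAP does not say so. A per-visit arm effect, or a model holding the arms equal at baseline, would also fit the text. Section 5.2.2 plans direct per-visit tests as well, and the 2/(1 + rho) ratio does not apply to those.
- *The model fails in the primary population.* This holds for status only, and only if the model is run there with week -8 as an outcome row. Section 3.3 does not clearly ask for that; among all enrolled the model fits.
- *The infection difference is never estimated in the PCR-positive group.* Section 3.3 speaks of all enrolled participants for the primary vaccine outcomes too, although those are restricted to PCR-positives. The same phrase for the malaria outcome therefore settles nothing, and the population is ambiguous.

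The lack of a stated reference visit, covariate set and population for this outcome still stands.

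**Conclusion.** The contradiction over testing week -8 is certain on the text. Beyond that, the GEE is under-specified. If it is a change contrast, it costs a variance factor of 1.67 to 1.33 against baseline adjustment for assumed rho of 0.2 to 0.5. Against the planned per-visit comparisons, adjustment gains a factor of 1.04 to 1.33 over the same range. All these factors assume a linear contrast with equal variances; the binary simulation agrees roughly at one correlation. Estimation failure in the PCR-positive group is conditional and limited to infection status.

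This concerns a secondary outcome and invalidates no planned comparison. It is worth correcting before analysis because the infection difference around vaccination is needed to interpret the primary result.

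**What to change.** 1. In sections 2.7 and 5.2.2 and in Table 6, present week -8 malaria status and intensity by arm descriptively, without P values.
2. In section 5.2.2, fit the GEE to post-randomisation visits only, with arm, visit, arm-by-visit and the week -8 value (status or intensity) as covariate, and report a DP-placebo estimate at each visit. State the link and effect measure: with a logit link, adding the covariate turns the odds ratio into a conditional one, so a risk difference standardised over week -8 status may be easier to read. Settle the visit list as well, since section 3.3 also names week 28 and section 2.7 and Table 6 do not. This step assumes that week 0 follows randomisation, which the SAP does not state.
3. State that the analysis covers all enrolled participants, and repeat the weeks 0, 4 and 8 comparison in the baseline PCR-positive group. Drop week -8 status there, because it is constant. Report the result beside the primary vaccine results.

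The cost is SAP wording and one extra table from data already collected. Estimates in the PCR-positive group will be less precise: with 60% of participants and equal outcome variance, standard errors are about sqrt(1/0.6) = 1.29 times those for all enrolled.

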# Shell table shows weeks -8 and 0 only for reasons of space in this document; additional columns in the same format as that shown for weeks -8 and 0 will be included for weeks 4, 8 and 52.

\*P values reported from chi square test

\*\* Estimate and P value from GEE
